Protocol Title:

Double-Blinded Randomized Control Trial Comparing Liposomal Bupivacaine and Bupivacaine Hydrochloride in Transversus Abdominis Plane Blocks Prior To DIEP Flap for Breast Reconstruction

Protocol Version Date:

10/01/2018

NCT # 03700970

Principal Investigator:

[name] – Professor, Department of Plastic Surgery, Vanderbilt University Medical Center
[name]

Sub-Investigators:

[name] [name] – Assistant Professor, Department of Anesthesiology, Vanderbilt University Medical Center
[name] [name] – Professor, Department of Anesthesiology, Vanderbilt University Medical Center
[name] – Associate Professor, Department of Plastic Surgery, Vanderbilt University Medical Center
[name] – Department of Plastic Surgery, Vanderbilt University Medical Center

Background

Perioperative and postoperative analgesia is a high priority for patients undergoing plastic and reconstructive surgery. It is of particular interest in patients undergoing abdominally-based free flaps for breast reconstruction (e.g., deep inferior epigastric artery perforator flaps) that includes excision of abdominal skin and subcutaneous tissue since the majority of pain after these operations is derived from the abdominal donor site (Jablonka et al, PRS 2017). Although intravenous and oral opioids have been the mainstay of postoperative pain control for this patient population, they are associated with a number of detrimental effects that can delay recovery and increase length of hospital stay. For example, they can lead to nausea, vomiting, constipation, lethargy, cough suppression, confusion, and orthostatic hypotension (Pizzi et al; Pharmacotherapy 2012). By reducing these side effects, resumption of a normal diet and ambulation can be achieved faster, which can accelerate recovery. This in turn can lead to decreased length of hospital stay and its associated cost, as well as improvement in the perceived quality of life for this patient population.

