Local analgesia, in the form of transversus abdominis plane (TAP) block that is administered in the operating room prior to the incision under ultrasound guidance, has been advocated to provide improved analgesia in the perioperative and postoperative periods. This is a promising approach that can decrease or even eliminate the need for narcotics in the postoperative period. This is a standard procedure at VUMC, and part of the Enhanced Recovery Pathway, for patients undergoing abdominally-based free flap breast reconstruction. However, there is debate regarding the best local anesthetic for these purposes. Liposomal bupivacaine has been used widely and is believed to provide adequate analgesia for more than 48 hours after surgery. On the other hand, plain bupivacaine is significantly cheaper and has also been shown to have promising and lasting analgesic results. To date, there are not randomized trials comparing the two local analgesics in a well-defined group of plastic surgery patients in general and also specifically in patients undergoing abdominally-based free flap breast reconstruction.

Rationale and Specific Aims

This study is designed to compare the efficiency of TAP blocks using liposomal bupivacaine versus plain bupivacaine that is administered in the operating room under ultrasound guidance prior to the incision in patients undergoing abdominally-based free flap breast reconstruction.

The ***primary aim*** of the study will be to compare the amount of supplemental postoperative narcotic analgesia (both intravenous and oral) required by the study groups in oral morphine equivalents from postoperative days 0 to 7. The amount of postoperative analgesia will be documented daily until postoperative day 7. It will be obtained from the medical records during hospitalization, and with daily phone calls after the patients get discharged with instructions to document this data daily.

The *secondary aims* will be:

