Patients eligible for the study will be seen by the participating attendings at Vanderbilt University Medical Center, or one of their associates. The patient will be told about the study and given an opportunity to read the consent. If they wish to participate, they will be asked to sign the consent.

Participants will be randomized to receive liposomal bupivacaine or plain bupivacaine in a permuted block fashion, in block of sizes 2 or 4. For each block, block size will be selected uniformly at random. This method of randomization ensures balance between groups following every second or fourth allocation. The patients will be randomized after providing written informed consent in the outpatient clinic. Following randomization, the plastic surgeons performing the surgery and assessments will be blinded to study treatment arm. Patients will also be blinded to the study treatment arm. The anesthesia team and some of the ancillary research staff will not be blinded to study treatment arm.

Study Procedures

Patients randomly assigned to the liposomal bupivacaine group or plain bupivacaine group will receive this intervention intra-operatively prior to the initiation of surgery.

Local analgesia (TAP blocks) will be administered under ultrasound guidance in the operating room after the patient is intubated and under general anesthesia. Transfascial injections will be performed by the anesthesiologist using an epidural needle. Under sterile conditions and ultrasound guidance, the fascial plane between the internal oblique and transversus abdominis muscles (muscles of the abdominal wall) will be identified at the anterior axillary line, midway between the costal margin and iliac crest. The epidural needle will be inserted through the skin to the appropriate fascial plane, and the local anesthetic will be injected in that plane. Then the needle will be removed and discarded, and the patient will be prepped and draped to start the surgery.

Liposomal bupivacaine group: 20mL of Exparel® 1.3% mixed with 20mL of 0.25% bupivacaine, for a total of 40mL of local anesthetic mixture, 20mL to be injected on each side.

Regular bupivacaine group: 20mL of 0.25% bupivacaine injected on each side.

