The Anesthesia team will follow standard care procedures regarding perioperative pain management (including preoperative, intraoperative, and postoperative analgesic regimens). Patients in all groups will also receive instructions in the preoperative period dictating the recommended approach to postoperative pain control.

Risks

Injection with the local anesthetic may cause participants to experience some discomfort, redness or a small bruise at the site of the injections. These will be temporary and will disappear in a couple of days.

With any nerve block there is a very small possibility of damage to the nerve, which could result in numbness of the surrounding area. According to the medical literature the likelihood of this injury is 1 in 10000 to 1 in 100000.

In rare cases the local anaesthetic may be absorbed into the bloodstream. In such rare scenario, the systemic absorption of the local anaesthetic may cause one of the following side effects:

- Slow-irregular heartbeats, low blood pressure, abnormal heartbeats, and cardiac arrest (2.3 events every 100,000 patients).
- Toxicity to the brain, including seizures (13.7 events every 100,000 patients);
- Respiratory arrest (4.6 events every 100,000 patients).

The blocks are performed in a monitored setting in the operating room. Patients are connected to monitors including blood pressure cuff, ECG and oxygen saturation. These monitors allow close monitoring for any signs of local anesthetic toxicity. The area is equipped with all resuscitation medication and equipment, and personnel are adequately trained in treatment of these complications.

Blocks are performed under direct ultrasound guidance so full visualization of the needle and the local anesthetic is observed. This will protect against nerve injury.

Reporting of Adverse Events or Unanticipated Problems involving Risk to Participants or Others; Study Withdrawal/Discontinuation

The progress of the study will be discussed formerly at regularly scheduled research meetings. These will serve as a forum for the voicing of concerns or problems with the study. If participant safety is a concern, the research investigators will immediately notify the P.I. Adverse events will be reported to the IRB according to IRB policies and procedures, as there are specific guidelines at IRB Policy and Procedure III.L.1 that must be followed.

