Local anesthetic toxicity or nerve injury will be considered serious adverse events. Also allergic reactions to the local anesthetic will be considered adverse events. These patients will be withdrawn from the study and appropriate treatment will be instituted. The anesthesia care team will identify such an event and report it.

Statistical Considerations

Sample size calculations were based on demonstrating superiority of the TAP block with liposomal bupivacaine.

The sample size calculation for the oral morphine equivalent requirements was based on one of our previous studies on Enhanced Recovery Pathway for free flap breast reconstruction. Calculations showed that randomizing 60 patients will obtain 80% power to detect a difference between the two groups.

Privacy/Confidentiality Issues

Collected data will be stored in a password protected REDCap™ database with sole access delineated by the investigators and study personnel of the study.

Follow up and Record Retention

The data will be extracted from the EMR via of EPIC (eStar) and entered in a RedCap™ database. Paper copies of the surveys will be kept in a locked cabinet by the investigators of the study until study completion of all data analysis and then subsequently securely destroyed.

Collected data will include demographics, amount of supplemental postoperative narcotic analgesia both intravenous and oral, visual analog pain scale, time to return of bowel function, time to first opiate use, incidence of narcotic complications, and Quality of Life. Some of these variables will be collected at several times points as described above.

Records will be retained for 6 years following the study completion.

References

Practice guidelines for acute pain management in the perioperative setting. A report by the American Society of Anesthesiologists Task Force on Pain Management, Acute Pain Section. *Anesthesiology*. 1995; 82(4):1071-81.

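### Does the lack of a rule on who makes the daily calls and extracts the opioid data undermine the blinding of the primary endpoint?

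*Protocol*

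**What the plan says.** The protocol title calls the trial "Double-Blinded Randomized Control Trial Comparing Liposomal Bupivacaine and Bupivacaine Hydrochloride". Enrollment/Randomization then says who is blinded. On the clinical side, "Following randomization, the plastic surgeons performing the surgery and assessments will be blinded to study treatment arm", and patients are blinded as well. The exception is disclosed in the same paragraph: "The anesthesia team and some of the ancillary research staff will not be blinded to study treatment arm".

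Rationale and Specific Aims defines the primary endpoint as intravenous and oral opioid use in oral morphine equivalents on days 0 to 7. On the source of these data it says: "It will be obtained from the medical records during hospitalization, and with daily phone calls after the patients get discharged". Patients are told to document their use daily. Follow up and Record Retention describes extraction from the electronic record into the study database without naming a role. Privacy/Confidentiality Issues describes the database as one "with sole access delineated by the investigators and study personnel of the study", with no split by knowledge of arm.

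Two further sentences concern the unblinded anesthesia team. Study Procedures says: "The Anesthesia team will follow standard care procedures regarding perioperative pain management (including preoperative, intraoperative, and postoperative analgesic regimens". On toxicity, nerve injury and allergic reactions, the adverse-event section says: "The anesthesia care team will identify such an event and report it". The SAP is silent on the blinding of data collectors.

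**The concern.** In a trial described as double-blinded, one expects whoever records the primary endpoint not to know the arm. Here some research staff do know it, no text limits their tasks, and calling patients and abstracting charts is work that research staff plausibly do. The one sentence that mentions blinded assessments is about plastic surgeons, and nothing says that surgeons make the calls or extract the records.

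Judgement can enter when a vague phone report is probed, when a missing day is handled, and when intravenous and oral doses are converted to morphine equivalents. A collector who knows the arm could settle such cases differently by arm. With 60 patients and a planned 20% reduction, a systematic difference in recording would either inflate the false-positive rate or hide a real effect.

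A second worry is that the unblinded anesthesia team is named in connection with postoperative analgesic regimens. Knowledge of the arm might then affect opioid use itself and not only its recording.

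**Working it through.** **Reading the text.**

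1. Does the plan assign collection to unblinded staff? No. The calls and the extraction are described without an actor.
2. Does it leave blinded people to do the work? Very probably. Only some of the ancillary staff are unblinded, which implies that others are not.
3. Is the double-blind label contradicted? No. Patients and operating surgeons are blinded, and the unblinded groups are named openly.
4. Could the blinded assessments include the calls? Possibly. The third exclusion criterion speaks of follow-up assessments in which patients take part, and daily calls would fit that description. This reading is not conclusive, and it does not clearly reach chart extraction.
5. Do the two statements about the anesthesia team conflict? No. One says that the team knows the arm; the other says that it follows standard care. Patients in all groups also receive instructions on postoperative pain control.

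**The plan's own figure.** The SAP gives 60 participants for 80% power, a 20% reduction, and coefficients of variation of 20% (between subjects) and 60% (within subjects). On the log scale the variances are ln(1 + 0.20²) = 0.0392 and ln(1 + 0.60²) = 0.3075, and the planned effect is −ln(0.8) = 0.223. The SD of a subject's mean over d days is √(0.0392 + 0.3075/d). By normal approximation with 1:1 allocation:

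- 4 days: N = 74 two-sided, 58 one-sided
- 6 days: N = 58 two-sided
- 8 days: N = 50 two-sided

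The figure of 60 is therefore reachable, but only with choices that the SAP does not state. The present point is about conduct and does not depend on which choice was made. It uses only the variances.

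**Size of a collection bias.** Take 30 per arm, a two-sided 0.05 test and the noncentral t distribution with 58 degrees of freedom. The log-scale analysis and the two-sided test are assumptions: the SAP mentions the log transformation only under sample size and does not state sidedness.

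- SE of the log ratio = √[(2/30)(0.0392 + 0.3075/d)] = 0.0720 for 8 days (days 0 to 7) and 0.0745 for the SAP's 7 days.
- Let a share u of person-days be unclear, and let those days be resolved a fraction r lower in one arm. The bias on the log scale is u × ln(1 − r). Both u and r are assumed; the documents give neither.

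Results for 8 days. The last column has a true 20% reduction with the bias acting against it; without bias, power is 86.2%.

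| u | r | Bias (log) | Shift in recorded use | Bias ÷ SE | False-positive rate | Power, adverse direction |
|---|---|---|---|---|---|---|
| 5% | 10% | 0.0053 | 0.5% | 0.07 | 5.1% | 84.6% |
| 10% | 10% | 0.0105 | 1.05% | 0.15 | 5.2% | 82.8% |
| 5% | 25% | 0.0144 | 1.4% | 0.20 | 5.4% | 81.4% |
| 10% | 25% | 0.0288 | 2.8% | 0.40 | 6.8% | 75.7% |

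As a share of the planned log effect, the bias runs from 0.0053/0.223 = 2.4% to 0.0288/0.223 = 13%. With 7 days the false-positive rates are 5.1% to 6.7%.

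**The case for a change.** The strongest case for a change is that the gap is real and cheap to close. No passage bars unblinded staff from the calls or the extraction, and the sentence on surgeons does not settle who does that work. One sentence naming blinded collectors would need no new data and would mainly reallocate existing tasks. If the record displays the block drug, even a nominally blinded extractor might learn the arm. Larger biases can also be imagined: an assumed 10% shift on 4 of 8 days gives a false-positive rate of about 11%, and on 4 of the SAP's 7 days about 12.5%.

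The silence stands, and so does the usefulness of recording the delegation somewhere. The rest is weaker. The larger error rates require a shift in every patient of one arm on half or more of the days, and the documents offer no mechanism for that. Whether the record shows the block drug is not stated, so a masked listing would answer a problem that nobody has shown to exist. Whether enough blinded staff are available for daily calls is likewise unknown, so the cost is not clearly nil. The point about the anesthesia team identifies no contradiction to reconcile. That team gives the block and watches for toxicity, so its knowledge of the arm is an understandable trade-off.

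**Conclusion.** The concern describes an unwritten delegation rule, not an error. A team following the plan as written can have blinded staff make the calls and extract the data, and nothing in the documents pushes it the other way. A site would normally settle this when it assigns tasks, so no change to the protocol or SAP is needed.

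If unblinded staff did collect the data, the illustrated collection scenarios shift recorded use by 0.5% to 2.8% against a planned 20% reduction. The false-positive rate would be about 5.1% to 6.8%. In the adverse direction power would fall from 86.2% to between 84.6% and 75.7%. The top of that range is not trivial, but it needs one day in ten to be unclear and those days to be resolved 25% lower in one arm. The figures rest on assumed shares and differences, a log-scale analysis, a two-sided test, complete data and the SAP's coefficients of variation. They show what a lapse in conduct might cost; they are not evidence that the plan produces one. The conclusion would change if a delegation record showed that staff who knew the arm made the calls or converted the doses.

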Study Title: Double-Blinded Randomized Control Trial Comparing Liposomal Bupivacaine and Plain Bupivacaine in Transversus Abdominis Plane For Deep Inferior Epigastric Artery Perforator (DIEP) Flap Breast Reconstruction

NCT # 03700970

Document date: October 1, 2018

Statistical Analysis

Patient characteristics were summarized as appropriate, using mean (standard deviation [SD]) and median (25th-75th interquartile range [IQR]) for quantitative variables and counts (percentages) for qualitative variables. Unadjusted comparisons of patients between the plain bupivacaine group and the liposomal bupivacaine group were performed using Wilcoxon test or Pearson chi-square test. The effect of the study intervention on daily oral opioid intake in oral morphine equivalents (OME) was examined using linear mixed effects regression model, adjusting for post-operative day (as a categorical variable), intervention status (plain bupivacaine/ liposomal bupivacaine), and their interaction. Since there were repeated measurements of OME for 7 post-operative days, a random intercept indexed by subject number was used in the linear mixed effects regression model. All analyses were performed using the R Programming Language 3.3.0 (R Foundation for Statistical Computing, Vienna, Austria). P<0.05 was considered a statistically significant difference.

Sample size calculations were based on demonstrating superiority of the TAP block with liposomal bupivacaine. A simulation-based power analysis was used to evaluate statistical power under the following assumptions: 1) use of linear mixed effects regression after log transformation of the opioid intake outcome, 2) average opioid consumption on days 0, 1, 2, and

3 is 30, 90, 70 mg mEq under standard of care, 3) use of liposomal bupivacaine will result in a 20% reduction in opioid consumption at each study day, and 4) the between- and within-subjects coefficients of variation are 20% and 60%, respectively (these values are based on standard of care data from our institution). Thus, the minimum-detectable difference is a 20% reduction in average opioid consumption at each study day. Under these assumptions, 60 participants are needed to achieve 80% power.

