- 1) Pain control, as measured by a visual analog NPS number ranging from 0 (no pain at all) to 10 (worst pain ever) between the 2 groups. This will be evaluated immediately after surgery in the postanesthesia care unit (PACU), on the day of surgery and all subsequent postoperative days until discharge and on postoperative day 7. In the PACU patients will be asked about their current pain. For the inpatient postoperative days and postoperative day 7, patients will be asked to record their average, current, and maximum Numeric Pain Scale (NPS) score for the previous 24 hours
- 2) Time to first opiate use: time from end of surgery (i.e. patient went to recovery or ICU) until time of first opioid intake)
- 3) Time to return of bowel function: time from end of surgery (i.e. patient went to recovery or ICU)
- 4) Incidence of narcotic complications (i.e. nausea, vomiting, constipation, urinary retention, dizziness, etc.); defined as the number of occurrences of the complication per day for the first 7 days after surgery
- 5) Quality of life (QoL) as measured with:
Baseline (during consenting before surgery): WHODAS, QoR-15, PROMIS-29
0-7 days: QoR-15
Day 7 and 14: PROMIS-29
Day 30: PROMIS-29, WHODAS

Inclusion/Exclusion Criteria

Inclusion criteria will include:

- 1) age between 18-85 years
- 2) males or females
- 3) plastic surgery for abdominally-based free flap breast reconstruction.

Exclusion criteria will include:

- 1) those not candidates for TAP blocks due to allergies to the medications (e.g., bupivacaine)
- 2) those with anatomic contra-indications to performing a TAP block
- 3) those unwilling to participate in follow-up assessments
- 4) vulnerable populations
- 5) chronic pain or associated diagnosis

Enrollment/Randomization

Patients undergoing abdominally-based free flap breast reconstruction under general anesthesia will be randomized to receive a TAP block with either liposomal bupivacaine or plain bupivacaine to determine if narcotic requirements and/or pain control is better achieved with one of the above methods. Patients in this study will be recruited in the plastic surgery outpatient clinics. No advertising will be done and there will be no recruitment tactics.

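### WHODAS, QoR-15 and PROMIS-29 are measured before surgery, but no between-arm method in the SAP uses these baselines; adjusting for them is a cheap, minor gain in precision

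*SAP*

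**What the plan says.** Secondary aim 5 in the protocol is quality of life. Its schedule opens with "Baseline (during consenting before surgery): WHODAS, QoR-15, PROMIS-29". Each instrument is then repeated: QoR-15 on days 0 to 7, and the other two as "Day 7 and 14: PROMIS-29" and "Day 30: PROMIS-29, WHODAS".

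The Enrollment/Randomization section states: "The patients will be randomized after providing written informed consent in the outpatient clinic". The block itself is given in the operating room, and patients are blinded to arm.

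The SAP's Statistical Analysis section states two kinds of between-arm method. The general one is: "Unadjusted comparisons of patients between the plain bupivacaine group and the liposomal bupivacaine group were performed using Wilcoxon test or Pearson chi-square test". The other is the opioid model: "The effect of the study intervention on daily oral opioid intake in oral morphine equivalents (OME) was examined using linear mixed effects regression model". Its terms are post-operative day, arm, their interaction and a random intercept per subject. The SAP does not mention quality of life or any of the three instruments, and it contains no baseline covariate and no change from baseline.

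The sample size concerns opioid intake only. The protocol's Statistical Considerations say: "The sample size calculation for the oral morphine equivalent requirements was based on one of our previous studies".

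**The concern.** A baseline score of the same instrument is often the best available predictor of the follow-up score, and here it is already collected. It is also a legitimate covariate: it is taken at consent, before the block, from patients who do not know their arm. Leaving it out means that differences between patients that existed before surgery stay in the error term.

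The point is specific to aim 5, the only secondary aim with a pre-surgery measurement. Pain is first recorded in the PACU, and the two time-to-event outcomes and the complication counts start after surgery. With about 30 patients per arm and no power claim for quality of life, precision on this aim is limited to begin with.

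**Working it through.** **The plan's own figure.** The only one is 60 participants for 80% power on opioid intake; none exists for quality of life. On the subject mean of log intake, with difference ln(0.8) = -0.223 and variance (between + within/days), two readings come close to 60:
- 4 days, CVs converted by ln(1 + CV²), one-sided 0.05: SD = √(0.0392 + 0.3075/4) = 0.341, N = 58, power at 60 = 81.4%.
- 7 days, CVs taken as log-scale SDs, two-sided 0.05: SD = √(0.04 + 0.36/7) = 0.302, N = 58, power at 60 = 81.5%.

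Other readings do not (for example, 4 days two-sided with converted CVs gives N = 74). Nothing below depends on this; only N = 60, split 30 and 30 by the balanced blocks, is carried forward.

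**One follow-up.** Let rho be the correlation between baseline and follow-up. It is not in the documents, so a range is assumed. Adjustment multiplies the variance of the arm difference by (1 - rho²) × (1 + 1/56), where the second term is the average cost of estimating one covariate with N = 60. The detectable difference at 80% power, two-sided 0.05, is (1.960 + 0.842) × √(2/30) = 0.72 SD unadjusted. It is then multiplied by the square root of the factor.

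| rho (assumed) | 1 - rho² | Net variance factor | Equivalent N (60/factor) | Detectable difference (SD) |
|---|---|---|---|---|
| 0 | 1.00 | 1.018 | 59 | 0.73 |
| 0.2 | 0.96 | 0.977 | 61 | 0.72 |
| 0.3 | 0.91 | 0.926 | 65 | 0.70 |
| 0.5 | 0.75 | 0.763 | 79 | 0.63 |
| 0.7 | 0.51 | 0.519 | 116 | 0.52 |

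Break-even: 1 - rho² = 56/57, so rho = √(1/57) = 0.13.

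**Day-averaged effect.** If rho is the same at every visit and the day-to-day correlation is c, the correlation of baseline with the mean of k visits is rho / √((1 + (k - 1)c)/k). For c from 0.5 to 0.7 (assumed) and rho 0.2/0.3/0.5, the net factors are:
- QoR-15, k = 8: 0.945–0.963 / 0.855–0.894 / 0.565–0.673.
- PROMIS-29, k = 3: 0.957–0.967 / 0.880–0.903 / 0.636–0.700.

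A constant rho is a further assumption: a pre-surgery score may relate differently to the day of surgery and to a week later.

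**Simulation.** With normal scores, 30 per arm, an assumed 0.5 SD difference and 4,000 runs per setting, Wilcoxon power was 44–45% throughout. ANCOVA gave 46% at rho = 0 and 51%, 58% and 76% at rho 0.3, 0.5 and 0.7. Type I error was 4.5–5.2% across both methods. The one to two points at rho = 0 reflect the use of normal-theory rather than rank methods on normal data, not the baseline.

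**The case against.** The strongest objection is that the Wilcoxon sentence may have nothing to do with quality of life. It directly follows the sentence on summarising patient characteristics and refers to comparisons of patients, so it may describe only the table of characteristics. This stands. A reader might infer that the SAP assigns Wilcoxon tests to the quality-of-life scores, and the documents do not settle that. On the narrower reading no quality-of-life method is stated at all, which is a separate and larger gap. On either reading no stated method uses the baselines.

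Second, the size of the gain rests wholly on an assumed rho. This also stands: at 0.2 to 0.3 the gain is negligible to small, and nothing in the documents supports 0.5 or more.

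Third, missing baselines can undo the gain if those patients are dropped. At rho 0.2, 60 × 0.977 = 58.6, so losing 2 patients cancels it; at rho 0.3, 60 × 0.926 = 55.6, so losing 5 does. This stands, and it is why the fix includes a rule for missing baselines.

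Fourth, choosing an adjusted over an unadjusted valid test could be called preference. That limits the priority, but the possible loss is about 2% of variance against a gain that may be material.

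**Conclusion.** The point holds as a free or cheap improvement of minor priority. The baselines are collected, are legitimate covariates, and appear in no between-arm method in the SAP. At one follow-up the variance factor is about 0.98/0.93/0.76/0.52 for an assumed rho of 0.2/0.3/0.5/0.7, and 1.02 if the baseline carries no information.

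Two stronger conclusions are tempting and are not supported. A reader might infer that an unadjusted quality-of-life comparison is biased or invalid; under randomisation it is neither, and only precision is lost. A reader might also infer that the trial's main result or its size is in doubt; quality of life is a secondary aim, the sample size was set for opioid intake, and the primary analysis and N = 60 are untouched.

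**What to change.** For each quality-of-life score to be compared, pre-specify in the SAP a comparison adjusted for the pre-surgery score of the same instrument:
- WHODAS at day 30: ANCOVA with arm and baseline WHODAS.
- QoR-15 (days 0 to 7) and PROMIS-29 (days 7, 14 and 30): a mixed model with arm, day, arm-by-day and baseline score, with a random intercept per subject. This extends the structure that the SAP already uses for opioid intake. Name the day-averaged arm effect as the contrast.
- Take the estimate, 95% CI and p-value from the same model, so that they cannot disagree. A rank-based version with ranked baseline can be a sensitivity analysis if scores are skewed or at a ceiling.
- Keep patients with a missing baseline by a stated rule, such as simple baseline imputation.

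The mixed model is preferable to averaging whatever days are available. If scores rose linearly by an assumed 1.5 SD over days 0 to 7, a patient missing days 6 and 7 would have an average taken around day 2.5 instead of day 3.5, about 1.5/7 = 0.21 SD too low. Differences between arms on single days can also be reported; the baseline sharpens these too, although in balanced data its main effect does not sharpen the arm-by-day interaction.

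The cost is SAP wording, a few lines of code and one degree of freedom (about 2% more variance if the baseline is uninformative). No new data are needed.

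### The SAP's primary model is worded for oral opioid over seven days, but the protocol's primary outcome is intravenous plus oral opioid over POD 0 to 7 (eight daily values)

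*SAP*

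**What the plan says.** The protocol (Rationale and Specific Aims) sets the primary aim as a comparison of "supplemental postoperative narcotic analgesia (both intravenous and oral) required by the study groups in oral morphine equivalents from postoperative days 0 to 7". It adds: "The amount of postoperative analgesia will be documented daily until postoperative day 7". The data list under Follow up and Record Retention again names both routes: "amount of supplemental postoperative narcotic analgesia both intravenous and oral".

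The SAP (Statistical Analysis) has one sentence that defines the variable in the primary model. It names "daily oral opioid intake in oral morphine equivalents (OME"), modelled by day as a categorical factor, treatment arm and their interaction. The next sentence justifies the random intercept: "Since there were repeated measurements of OME for 7 post-operative days". Intravenous opioid is not mentioned anywhere in the SAP, and the seven days are not listed.

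**The concern.** The protocol and the SAP describe the same primary comparison with different routes and different day counts, and neither reconciles them.

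Three things are at stake.

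- **The test may not address the stated primary outcome.** An oral-only, seven-day variable is not the variable that the protocol promises to compare.
- **An oral-only outcome depends on route as well as on amount.** At equal total intake, an arm that moved earlier from intravenous to oral opioid would look worse.
- **The primary variable is not fixed.** Two readings of the routes and at least two of the days leave several candidate outcomes, and the SAP gives no rule for choosing among them before the data are seen.

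**Working it through.** **1. The definitions side by side**

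| Item | Protocol | SAP model sentences |
|---|---|---|
| Routes | intravenous and oral | oral |
| Unit | oral morphine equivalents | oral morphine equivalents |
| Days | POD 0 to 7 | 7 postoperative days, not listed |
| Daily values per patient | 7 − 0 + 1 = 8 | 7 |
| Patient-days for 60 patients | 60 × 8 = 480 | 60 × 7 = 420 |

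If the seven days are POD 1 to 7, the model omits day 0, which the SAP's own power assumptions count as a study day. If they are POD 0 to 6, it omits the last day of the protocol's window. Because day is categorical and interacts with arm, the day count also sets the fitted model: seven days give six interaction terms and eight give seven.

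**2. The plan's own sample size**

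Inputs from the SAP: 60 patients (30 per arm), a 20% reduction on each day, between- and within-subject CVs of 20% and 60%, a log-transformed outcome, and a significance level of 0.05 with sidedness not stated. For a treatment effect averaged over k days in a random-intercept model:

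- effect = −ln(0.8) = 0.2231
- SE = √[(2/30) × (σ_b² + σ_w²/k)]
- power ≈ Φ(effect/SE − 1.96) for a two-sided 0.05 test

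The CVs can be read in two ways:

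- lognormal: σ_b² = ln(1.04) = 0.0392, σ_w² = ln(1.36) = 0.3075
- CV squared: σ_b² = 0.04, σ_w² = 0.36

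The stated 60 patients for 80% power can be approximately reproduced in two ways. Seven days, CV squared and a two-sided test need 58 patients. Four days (the days 0 to 3 named in the power paragraph), lognormal variances and a one-sided test also need 58. With four days and a two-sided test it is not reproduced: 74 (lognormal) or 82 (CV squared) would be needed. The stated figure therefore does not show which days the analysis uses.

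**3. Effect of the missing day (two-sided, 60 patients)**

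| Variances | k | SE | Power, normal approximation | Power, simulated (20,000 runs) |
|---|---|---|---|---|
| Lognormal | 7 | 0.0745 | 85.0% | 83.7% |
| Lognormal | 8 | 0.0720 | 87.3% | 86.4% |
| CV squared | 7 | 0.0781 | 81.5% | 80.3% |
| CV squared | 8 | 0.0753 | 84.2% | 83.3% |

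The loss from using seven days is 2.3 to 2.7 points by the approximation and 2.7 to 3.0 points by simulation.

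**4. Effect of the route**

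The documents give no split between intravenous and oral use, so the actual effect cannot be computed. A break-even follows from the SAP's 20% effect:

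oral-only ratio = 0.8 × (oral share, liposomal ÷ oral share, plain)

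This equals 1 when the share ratio is 1/0.8 = 1.25. With assumed shares, for illustration only: if the plain arm takes 100 units with 40% oral, its oral intake is 40; if the liposomal arm takes 80 units with 50% oral, its oral intake is also 40. Shares of 60% and 75% behave the same way (60 and 60). With equal totals and shares of 40% and 50%, the liposomal arm would appear 25% higher.

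**The case against.** The strongest reply is that the SAP is loosely worded, not wrong. It attaches oral to intake only once; its power paragraph speaks of opioid intake and consumption with no route, and converting to oral morphine equivalents suggests that other routes are included. This makes total opioid a plausible reading, perhaps the likelier one. It does not settle the matter: the unit is also needed to put different oral opioids on one scale, and the route-neutral wording is in the sample-size paragraph, not in the sentence that defines the model.

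On the days, the seven-day phrase explains the random intercept and does not formally define a window. It could mean the day of surgery plus seven further days. That is possible, but the SAP does not say it.

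The protocol carries the same date and is explicit, so the room for choosing an outcome after the fact is modest. That stands, and it limits the weight of the point without removing the mismatch.

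Finally, the power figures describe an assumed test. The SAP does not say which contrast of its arm-by-day model is primary, its model sentence mentions no log transformation, and its power assumptions name days 0 to 3 only. The normal approximation is also slightly generous. All of this is fair. The figures are used here only to show that one day more or less has a small effect.

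**Conclusion.** The concern holds. As written, the SAP's primary model does not use the protocol's primary outcome: it names one of two routes and seven of eight daily values. Whether the analyst would actually leave out intravenous opioid is not known.

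The day discrepancy costs about 2 to 3 points of power and does not undermine the 60 patients. That assumes a day-averaged effect on the log scale, a constant 20% reduction on every day modelled, 30 patients per arm and a two-sided 0.05 test. The route discrepancy carries the main weight because it could change what is estimated. Its size is unknown, and the 1.25 break-even shows only how a bias could arise, not that one is likely. The point should be fixed because it concerns the definition of the primary variable.

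**What to change.** In the SAP's model sentence, define the outcome as *total postoperative opioid per day, intravenous plus oral, converted to OME, on each of POD 0, 1, …, 7 (eight values per patient)*. In the next sentence, replace the seven-day phrase with *eight days (POD 0 to 7)*.

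This changes two sentences and needs no new data, since the protocol already has both routes recorded daily through POD 7. The SAP is written in the past tense, so if any analysis has already been run, the sponsor should also confirm which routes and days it used and rerun it if they differ. The days 0 to 3 window in the power paragraph is a separate sample-size matter, which would need further inputs and a new simulation. It is not part of this change.
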